# 4.1.4 Safety and tolerability analysis

AEs incidence will be compared between the trial arms using Pearson's chi-squared test. In case of significant changes, a relative risk will be calculated (with 95% CI).

A tolerability level for every group will be calculated based on the AEs incidence and nature (in accordance with Section 2.3 of this Plan).

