# 1. Protocol synopsis

Trial title	A Prospective, Multicenter, Open, Randomized, Parallel Clinical Trial for Comparative Assessment of Efficacy and Safety of Angal, Lozenges [Menthol], 1  mg + 5  mg (Sandoz d.d., Slovenia), and ANTI-ANGIN ® FORMULA, Lozenges, 0.2  mg + 2  mg + 50  mg (OOO Valeant, Russia) in Treatment of Patients with Uncomplicated Acute Infectious and Inflammatory Diseases of the Pharynx Accompanied by a Sore Throat
Trial code	TE_004_ANG_LOZ
Sponsor	ZAO Sandoz
Study drug	Angal, lozenges [menthol], containing 1 mg of lidocaine hydrochloride and 5 mg of chlorhexidine dihydrochloride
Reference drug	ANTI-ANGIN ® FORMULA, lozenges, containing 0.2 mg of tetracaine hydrochloride, 2 mg of chlorhexidine diacetate, and 50 mg of ascorbic acid
Clinical trial phase	
Trial population	Up to 280 patients are planned to be included (randomized) into the trial (140 patients in every treatment arm) with probable withdrawal of not more than 10% patients during the trial. A minimal number of patients required for the statistical analysis is 256 (128 patients in every treatment arm) provided that they completed the trial according to the protocol.
Scheduled trial duration	Not more than 7 days: Screening/randomization/initiation of trial therapy: Day 1. Therapy duration: up to 5 days depending on the trial arm. A follow-up visit (on the phone): 2 days after the last scheduled visit to the trial site. Total enrollment duration: 8 months.
The number of trial sites	up to 20

Trial objective	This trial has been designed to evaluate the non-inferior therapeutic efficacy and safety of the study drug Angal, lozenges [menthol] 1 mg + 5 mg (Sandoz d.d., Slovenia), comparing to ANTI-ANGIN ® FORMULA, lozenges, 0.2 mg + 2 mg + 50 mg (OOO Valeant, Russia), in treatment of patients with uncomplicated acute infectious and inflammatory diseases of the pharynx accompanied by a sore throat.

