#### Secondary goals:

- Assessment of safety of Angal, lozenges [menthol], 1 mg + 5 mg (Sandoz d.d., Slovenia) administration of 1 lozenge with a not less than 2-hour interval, up to 6–10 times per day, for 4 days or until full recovery (whichever occurs first during 4 days of therapy), compared to ANTI-ANGIN® FORMULA, lozenges, 0.2 mg + 2 mg + 50 mg (OOO Valeant, Russia)—administration of 1 lozenge with a not less than 2-hour interval, up to 6 lozenges per day, for 5 days or until full recovery (whichever occurs first during 5 days of therapy) in the treatment of patients with uncomplicated acute Infectious and inflammatory diseases of the pharynx accompanied by a sore throat.
- Evaluation of adverse events (AEs) in the trial arms.
- The AEs rate comparison between the trial arms.

S. SANDOZ

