# 9.1.4 Safety parameters analysis

A descriptive part of the safety analysis will include an evaluation of incidences and two-sided CI 95% for the following parameters in every trial group:

- AEs: the incidence in total and for separate categories (according to MedDRA), for the trial and by groups;
- SAEs: the incidence in total and for separate categories (according to MedDRA), for the trial and by groups;
- Incidence of clinically significant changes of the physical examination results by visits and groups;
- Incidence of clinically significant changes of the laboratory results by visits and groups;
- Incidence of clinically significant changes of the vital signs (body temperature, BP, pulse rate, HR) by visits and groups;
- Incidence of clinically significant changes of the ECG parameters by visits and groups;
- Global tolerance evaluation during the trial by the Investigator and patient;

The Fisher's exact test will be used to compare incidences between the groups, and chi-square will be used to compare the global therapy tolerability by the Investigator and patient. The McNemar's test will be used to evaluate for the dynamic changes during the trial (before–after) for all the repeatedly evaluated incidences in every group.

In addition to the incidence, all the quantitative safety parameters will be presented in a table form (laboratory data, vital signs, ECG) by visits and groups. The difference will be evaluated using 2-way-ANOVA (group and visit numbers will serve as the relevant factors). The post-hoc criteria will be used in case of significant difference.

Safety analysis will be performed on the safety population.

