## 3.10 Significance level

All statistical analyses in this trial will be conducted at 95% significance level (a threshold p value for confirmation of statistical significance is below 0.05), except for the primary endpoint where a one-sided statistical criterion will be used with 95% significance level (a threshold p value is below 0.05). The two-sided statistical criteria will be used for all other parameters.

For the primary endpoint evaluation, 90% CI will be calculated for the proportions difference with further evaluation of its lower boundary limit.

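### The SAP compares AE incidence by Pearson's chi-square where the protocol names Fisher's exact test, and gives a between-arm relative risk only after a significant result; a minor inconsistency to correct

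*SAP*

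**What the plan says.** Comparing adverse event rates is one of the protocol's listed secondary goals: "The AEs rate comparison between the trial arms" (Protocol 3.2).

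Protocol 9.1.4 lists the safety incidences, with AEs and SAEs first, and then allocates the tests: "The Fisher's exact test will be used to compare incidences between the groups, and chi-square will be used to compare the global therapy tolerability" by investigator and patient. For between-arm comparisons, Fisher's test therefore covers AE incidence and chi-square is kept for the tolerability score.

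SAP 4.1.4 allocates differently: "AEs incidence will be compared between the trial arms using Pearson's chi-squared test". It gives no fallback for small counts and does not say whether a continuity correction applies. Its next sentence sets the reporting rule: "In case of significant changes, a relative risk will be calculated (with 95% CI").

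Fisher's test does appear in SAP 4.1.5 for qualitative parameters, but that section concerns laboratory and functional tests and does not reach AEs.

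Three other provisions bear on this:
- SAP section 1 says no change from the protocol is envisaged.
- Protocol 9.6 requires deviations from the statistical plan to be described and justified, in an amendment or in the final report. In the latter case the SAP must list them. This one is not listed.
- SAP 3.10 sets the criterion for the AE comparison: "a threshold p value for confirmation of statistical significance is below 0.05", and "The two-sided statistical criteria will be used for all other parameters".

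**The concern.** Two analysts who each followed one of the governing documents could report different p-values for the same AE table. Because the relative risk depends on significance, they could also differ on whether any between-arm estimate is shown.

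The reporting rule is a problem in its own right. After a non-significant test, the planned output is a p-value beside two percentages, with nothing to show how large a difference the data still allow. That matters because the protocol's objective speaks of non-inferior efficacy and safety but sets no safety margin, so a between-arm interval is the natural way to show what has been excluded. After a significant test, the estimate has passed a filter that favours large values.

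**Working it through.** **Inputs.** 140 patients per arm (Protocol synopsis); two-sided 0.05 (SAP 3.10). Neither document gives an expected AE rate, so every rate below is an assumption, shown over a range. The plan has no AE figure to reproduce.

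**1. One table by hand: 5 v 0 events.**
- Uncorrected Pearson: X² = N(ad − bc)² / (product of the four margins) = 280 × (5×140 − 135×0)² / (5 × 275 × 140 × 140) = 137,200,000 / 26,950,000 = 5.09, p = 0.024.
- With continuity correction: 280 × (700 − 140)² / 26,950,000 = 3.26, p = 0.071.
- Fisher, two-sided: 2 × (140×139×138×137×136) / (280×279×278×277×276) = 0.060.

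**2. Other borderline tables.**

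| Events | Pearson, uncorrected | Pearson, corrected | Fisher |
|---|---|---|---|
| 4 v 0 | 0.044 | 0.131 | 0.122 |
| 5 v 0 | 0.024 | 0.071 | 0.060 |
| 7 v 1 | 0.031 | 0.073 | 0.066 |
| 9 v 2 | 0.031 | 0.065 | 0.060 |
| 17 v 7 | 0.033 | 0.055 | 0.053 |

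Across all tables with 0 to 44 events per arm, whenever the uncorrected test and Fisher's disagree at 0.05, Pearson is the significant one. With the correction, no table in that range disagrees with Fisher.

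**3. How often they disagree.** Exact binomial enumeration, uncorrected Pearson. The last column is computed before rounding.

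| Assumed AE rates | Pearson significant | Fisher significant | Disagree |
|---|---|---|---|
| 1% v 1% | 2.6% | 0.2% | 2.5% |
| 2% v 2% | 4.5% | 1.0% | 3.5% |
| 5% v 5% | 4.8% | 2.3% | 2.5% |
| 10% v 10% | 4.8% | 3.2% | 1.7% |
| 8% v 5% | 16.5% | 11.4% | 5.1% |
| 10% v 5% | 34.5% | 27.3% | 7.2% |
| 6% v 2% | 39.5% | 27.8% | 11.7% |

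**4. What the reporting rule leaves out.** Take 10 v 5 events. Fisher p = 0.29 and uncorrected Pearson p = 0.18, so no relative risk is due. It would be 10/5 = 2.0. The standard error of its log is √(1/10 − 1/140 + 1/5 − 1/140) = 0.535, so the 95% CI is exp(0.693 ± 1.96 × 0.535) = 0.70 to 5.70. The data allow a more than fivefold excess, and the planned output has no between-arm interval to show it.

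**5. What the rule does to the values it lets through.** At 8% v 5% the true ratio is 1.6. The uncorrected test is significant in about 17% of simulated trials, and the median relative risk among those is 3.3. Selection weakens as power rises: at 20% v 10% (true ratio 2.0, significant in 66%), the geometric mean among significant results is 2.4.

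**The case against.** Four points can be made against this, and most of each stands.

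*The disagreement depends on an unstated setting.* Correct. The SAP names Pearson's test without saying whether it is corrected, and with a correction the quoted tables agree with Fisher's test. The mismatch between documents remains either way.

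*Pearson is not the worse test.* A reader might infer that the SAP's choice is anti-conservative or could hide a safety signal. The calculations do not support that. At equal rates of 1% to 10%, the uncorrected test rejects in 2.6% to 4.8% of trials, so it holds its level, and it is the more sensitive of the two. Fisher's test is owed here because the protocol names it. Protocol 9.6 also leaves room to keep Pearson with a documented reason.

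*The AE results are not withheld.* A reader might infer that AE estimates in general depend on significance. They do not. Protocol 9.1.4 requires per-arm incidences with two-sided 95% CIs, SAP section 4 does the same for qualitative variables, SAP Table 23 prints n/N (%) by arm, and Tables 21 and 22 break events down by severity and seriousness. Only the relative risk and its interval are conditional, and a reader could rebuild them from the counts.

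*Little hangs on it.* SAP section 4 ties the non-inferiority conclusion to the primary parameter alone and treats safety variables as exploratory. That stands, and it limits the severity. That non-significance would be taken as equal safety is a prediction about readers, which the documents can neither confirm nor refute.

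**Conclusion.** The allocation of tests is wrong as written: the SAP and protocol contradict each other on AE incidence, without the justification the protocol requires. The practical effect is small. Assuming an uncorrected chi-square, the tests disagree in about 2% to 5% of trials at equal rates of 1% to 10% or at 8% v 5%, in 7% at 10% v 5%, and in 12% at 6% v 2%, the largest of the cases tried. These rates are illustrative, since the documents give none.

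The conditional relative risk is a separate weakness, limited to that ratio and its interval. Reported values are inflated on average. It would go too far to say that each one is exaggerated, because selection acts on the distribution and fades as power rises.

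Severity is minor. The primary analysis and the sample size do not depend on this test.

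**What to change.** In SAP 4.1.4:
- Name Fisher's exact test for between-arm AE and SAE incidence, as in Protocol 9.1.4. Alternatively, keep Pearson's test, state whether a continuity correction is used, and document and justify the change under Protocol 9.6.
- Replace the conditional sentence with a commitment to report the between-arm risk difference and relative risk, each with 95% CI, for any AE, any SAE and related AEs, whatever the p-value. Where one arm has no events the ratio is zero or undefined, so the risk difference carries the comparison.

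The cost is two sentences in the SAP and one more table column. No further data are needed.

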# 4.1.5 Analysis of laboratory and functional tests results

A between group comparison of the vital signs changes (systolic blood pressure, diastolic blood pressure, breathing rate, heart rate, body temperature) revealed at every visit (Visits 1, 2, 3) as well as laboratory results and ECG changes incidence obtained at Visit 1 and Visits 2–3 is envisaged. In addition, significance of the changes will be evaluated for all repeatedly measured parameters.

The following laboratory parameters will be reviewed:

- Hematology
  - o Hemoglobin
  - o RBC
  - o ESR
  - o WBC
  - o Neutrophils
    - Juvenile
    - Stab
    - Segmented
  - o Eosinophils
  - o Basophils
  - o Monocytes
  - o Lymphocytes
- Biochemistry
  - o Total protein
  - o AST
  - o ALT
  - o Total bilirubin

ANOVA methods will be used to reveal a simultaneous influence of a group and time factors on the quantitative parameters.

The cross tables analysis will be used to reveal a correlation between the qualitative parameters (chi-squared test).

For the quantitative parameters, a comparison will be made by Student's t-test for the independent samples (in case of confirmation of hypothesis on normal variables distribution) or Mann–Whitney test (in case of rejection of hypothesis on normal variables distribution); for the qualitative parameters—using Fisher's exact test.

To evaluate significance of the intragroup changes during the trial for repeatedly measured parameters, the paired Student's t-test (in case of confirmation of hypothesis on normal variables distribution) or paired Wilcoxon signed-rank test (in case of rejection of hypothesis on normal variables distribution) will be used; for the qualitative parameters McNemar's test will be used.

# 5 Presentation of statistical analysis results

# 5.1 Table templates

## Table 1. Patient distribution

Patient distribution	Arm Number of patients (proportion, %)	Group Number of patients (proportion, %)
Included in the trial (screened)	n/N (%)	n/N (%)
Excluded at screening	n/N (%)	n/N (%)
Randomized	n/N (%)	n/N (%)
Discontinued prematurely	n/N (%)	n/N (%)
ITT population	n/N (%)	n/N (%)
PP population	n/N (%)	n/N (%)
Safety population	n/N (%)	n/N (%)

# Table 2. Demographic and anthropometric patients' characteristics

Arm	Parameter	Age	Body weight	Height
	n			
	М			
	SD			
	95% CI			
	Min.			
	Max.			
	Me			
	IQR			
	n			
	М			
	SD			
	95% CI			
	Min.			
	Max.			
	Me			
	IQR			
	р			

# Table 3. Patients distribution by sex

Arm	Men	Women
	n/N (%)	n/N (%)
	n/N (%)	n/N (%)
р		

# Table 4. Patients distribution by race

Race	Arm	Number of patients (proportion, %)	р
Caucasian		n/N (%)	
Caucasian		n/N (%)	
Negroid		n/N (%)	
Negroid		n/N (%)	
Asian		n/N (%)	
Asian		n/N (%)	
Unknown		n/N (%)	

	n/N (%)	
< Other >	n/N (%)	
< Other >	n/N (%)	

## Table 5. Social habits: alcohol abuse

	Arm	Number of patients (proportion, %)	р
Non-user		n/N (%)	
INOII-USEI		n/N (%)	
F		n/N (%)	
Former user		n/N (%)	
Current user		n/N (%)	
		n/N (%)	]

# Table 6. Social habits: smoking

	Arm	Number of patients (proportion, %)	р
Non-smoker		n/N (%)	
INON-SMOKET		n/N (%)	
F 1		n/N (%)	
Former smoker		n/N (%)	
Current smoker		n/N (%)	
Current smoker		n/N (%)	

# Table 7. The main vital signs (Visits 1, 2, 3)

Arm	Parameter	Systolic blood pressure	Diastolic blood pressure	Pulse rate	BR	Body temperature
	n					
	М					
	SD					
	95% CI					
	Min.					
	Max.					
	Me					
	IQR					
	n					
	М					
	SD					
	95% CI					
	Min.					
	Max.					
	Me					
	IQR					
	р					

# Table 8. ECG results (Visits 1, 2, 3)

Arm	Parameter	ECG n/N (%)
	Reference	
	Deviation	
	Reference	
	Deviation	

Arm	Parameter	Hemoglobin	RBC	ESR	WBC
	n				
	М				
	SD				
	95% CI				
	Min.				
	Max.				
	Me				
	IQR				
	n				
	М				
	SD				
	95% CI				
	Min.				
	Max.				
	Me				
	IQR				
	р				

# Table 9.Hematology (Visits 1, 2, 3)

# Table 10. WBC differential (Visits 1, 2, 3)

Arm	Parameter	Neutrophils, total	Juvenile	Stab	Segmented	Eosinophils	Basophils	Monocytes	Lymphocytes
	n								
	М								
	SD								
	95% CI								
	Min.								
	Max.								
	Me								
	IQR								
	n								
	М								
	SD								
	95% CI								
	Min.								
	Max.								
	Me								
	IQR								
	р								

# Table 11.Biochemistry (Visits 1, 2, 3)

Arm	Parameter	Total protein	ALT	AST	Total bilirubin
	n				
	М				
	SD				
	95% CI				
	Min.				
	Max.				
	Me				
	IQR				

n		
М		
SD		
95% CI		
Min.		
Max.		
Me		
IQR		
р		

# Table 12.A number of patients with normal and abnormal hematology parameters (Visits 1, 2, 3)

Arm	Parameter	Hemoglobin	RBC	ESR	WBC
	Reference				
	Deviation				
	Reference				
	Deviation				

## Table 13.A number of patient with normal and abnormal WBC differential results (Visits 1, 2, 3)

Arm	Parameter	Neutrophils, total	Juvenile	Stab	Segmented	Eosinophils	Basophils	Monocytes	Lymphocytes
	Reference								
	Deviation								
	Reference								
	Deviation								

# Table 14. A number of patient with normal and abnormal biochemistry parameters (Visits 1, 2, 3)

Arm	Parameter	Total protein	ALT	AST	Total bilirubin
	Reference				
	Deviation				
	Reference				
	Deviation				

# Table 15. Concomitant diseases

Organ, system	Arm	Number of diseases (proportion, %)
		n/N (%)

# Table 16. Concomitant therapy

Drug group	Arm	Number of prescriptions (proportion, %)
		n/N (%)

# Table 17. Evaluation of throat pain severity according to VAS

Arm	Parameter	Visit 1	Visit 2	Visit 3
	n			
	М			
	SD			
	95% CI			
	Min.			
	Max.			
	Me			
	IQR			
	n			
	М			
	SD			
	95% CI			
	Min.			
	Max.			
	Me			
	IQR			
	р			

# Table 18. TSS scores (Visits 1, 2, 3)

Arm	Amount of scores	Sore throat	Difficultyin swallowing	Salivation	Pharyngeal mucosa hyperemia	Fever
	0	n/N (%)	n/N (%)	n/N (%)	n/N (%)	n/N (%)
	1	n/N (%)	n/N (%)	n/N (%)	n/N (%)	n/N (%)
	2	n/N (%)	n/N (%)	n/N (%)	n/N (%)	n/N (%)
	3	n/N (%)	n/N (%)	n/N (%)	n/N (%)	n/N (%)
	0	n/N (%)	n/N (%)	n/N (%)	n/N (%)	n/N (%)
	1	n/N (%)	n/N (%)	n/N (%)	n/N (%)	n/N (%)
	2	n/N (%)	n/N (%)	n/N (%)	n/N (%)	n/N (%)
	3	n/N (%)	n/N (%)	n/N (%)	n/N (%)	n/N (%)
	р	n/N (%)	n/N (%)	n/N (%)	n/N (%)	n/N (%)

# Table 19. Frequency of the recovery criteria achievement (total TSS $\leq$ 2) by Visits 2, 3

Arm	Parameter	Visit 2	Visit 3
	Criterion is met		
	Criterion is not met		
	Criterion is met		
	Criterion is not met		

Arm	Parameter	Tolerability evaluation by the patient	Tolerability evaluation by the physician
	n		
	М		
	SD		
	95% CI		
	Min.		
	Max.		
	Me		
	IQR		
	n		
	М		
	SD		
	95% CI		
	Min.		
	Max.		
	Me		
	IQR		
	р		

# Table 20. Global evaluation of treatment tolerability (Visits 2, 3)

# Table 21. Registered adverse events occured after initiation of the trial therapy

	Mile	d AEs	Moder	ate AEs	Sever	re AEs	To	otal	Total
Description	Serious	Non-serious	Serious	Non-serious	Serious	Non-serious	Serious	Non-serious	Serious +
	Schous	Non-serious	Schous	i von-serious	Serious	Inoll-serious	Schous	Non-serious	non-serious
				Organ syst	tem				
	Organ system								

## Table 22. Registered adverse events occurred after initiation of the reference therapy

	Mile	d AEs	Moder	ate AEs	Seve	re AEs	Te	otal	Total
Description	Serious	Non-serious	Serious	Non-serious	Serious	Non-serious	Serious	Non-serious	Serious + non-serious
	•	•		Organ syst	tem			•	
Organ system									

# Table 23. AEs frequency by the nosological groups

Nosological group	Arm	Arm	р
Nosological group 1	n/N (%)	n/N (%)	
Nosology 1	n/N (%)	n/N (%)	

Nosology 2	n/N (%)	n/N (%)	
Nosology 3	n/N (%)	n/N (%)	
Nosological group 1	n/N (%)	n/N (%)	
Nosology 1	n/N (%)	n/N (%)	
Nosology 2	n/N (%)	n/N (%)	
Nosology 3	n/N (%)	n/N (%)	

#### Table 24. Compliance evaluation

Arm	Parameter	Compliance
	n	
	М	
	SD	
	95% CI	
	Min.	
	Max.	
	Me	
	IQR	
	n	
	М	
	SD	
	95% CI	
	Min.	
	Max.	
	Me	
	IQR	
	р	

#### 5.2 List of figures

# Figure 1. TSS scores changes by visits and trial arms

For the parameters listed below: pharyngalgia, difficulty in swallowing, salivation, hyperemia of pharyngeal mucosa, and body temperature increase, as well as for total sum of scores

Figure 2. Difference in proportions of patients who achieved efficacy criteria in every arm, 90% CI

Figure 3. Incidence of TSS scores decrease for 50% or more in the trial arms

Figure 4. A period of time required for disease signs resolution according to the patient's diary and the trial arms

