# 3.8.3 Trial completion visit for Group B patients (Visit 3, Day 5)

This visit is for Group B patients only (ANTI-ANGIN® FORMULA) who did not achieve the recovery criteria (total TSS  $\leq$  2) at Visit 2 (Day 4).

Visit 3 is conducted on Day 5; the patient must visit the trial site in the fasted state and bring the filled-in diary and unused drug.

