## Figure 6. Dynamic changes of pharyngalgia severity according to VAS by visits and trial arms

Figure 7. Dynamic changes of vital parameters by visits and trial arms

For the vital signslisted below: systolic blood pressure, diastolic blood pressure, pulse rate, breathing rate, body temperature.

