#### Figure 8. Dynamic changes of hematology parameters by visits and trial arms

For the parameters listed below: Hb, RBC, ESR, WBC, neutrophils (juvenile, stab, segmented), eosinophils, basophils, monocytes, lymphocytes.

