# Figure 9. Dynamic changes of biochemistry parameters by visits and trial arms

For the parameters listed below: total protein, AST, ALT, total bilirubin.

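### Visit 3 holds only unrecovered Group B patients, yet the SAP tabulates and plots results by arm through Visit 3, so the comparator point describes a selected subset and can rise although every patient improves

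*SAP*

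**What the plan says.** SAP 3.8.3 defines Visit 3 (Day 5): "This visit is for Group B patients only", namely those whose total TSS was still above 2 at Visit 2. Footnote 3 to the visit schedule (protocol 4.2.3.1, Table 1) agrees. Group A and recovered Group B patients make their last scheduled site visit at Visit 2 (Day 4).

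The displays take no account of this:

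- In SAP 5.1, Table 17 ("Evaluation of throat pain severity according to VAS") gives both arms columns for Visits 1, 2 and 3 and has a p row. Table 18 (TSS) covers the same three visits and also has a p row. Tables 7 to 14 (vital signs, ECG, hematology, WBC differential, biochemistry) run over the same visits.
- SAP 5.2 lists "Figure 1. TSS scores changes by visits and trial arms" as the TSS display and "Figure 6. Dynamic changes of pharyngalgia severity according to VAS by visits and trial arms" as the VAS display. Three safety figures share that layout: vital signs in "Figure 7. Dynamic changes of vital parameters by visits and trial arms", blood counts in "Figure 8. Dynamic changes of hematology parameters by visits and trial arms" and blood chemistry in "Figure 9. Dynamic changes of biochemistry parameters by visits and trial arms".

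SAP 3.6 carries the last TSS forward only in an additional analysis of the primary endpoint and uses all other data as observed. SAP 4.1.5 compares vital signs between groups at each of the three visits and applies ANOVA to group and time. Protocol 9.1.4 names a two-way ANOVA with group and visit number as factors.

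Protocol Table 1 restricts Visit 2 hematology, biochemistry and ECG to Group A and recovered Group B, and SAP 3.8.2 agrees. TSS and VAS carry no such restriction. For vital signs the documents disagree: Table 1 marks them as restricted, while protocol 4.2.4.2 and SAP 3.8.2 list them for both groups.

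**The concern.** Between Visit 2 and Visit 3 the patients behind the Group B line change, and they change according to outcome. At Visit 2 the TSS and VAS points describe the whole arm. At Visit 3 they describe only those who had not recovered, while Group A has no point at all. A reader could take a change in who is measured for a change in how patients fare, in an open-label trial where the shift would usually make the comparator look worse.

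For laboratory data and ECG the fault is different. The two post-baseline Group B points share no patients, and the Visit 2 between-arm comparison sets all of Group A against recovered Group B.

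**Working it through.** The plan gives no figure to reproduce, so the check is arithmetic on observed means.

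**Inputs**

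- Group B size: 140 randomized (protocol 9.2).
- r, share of Group B recovered (total TSS of 2 or less) at Visit 2: not given. Assumed 40% to 80%. The mid-range 63% is borrowed from the expected comparator rate in protocol 9.2, which is for absence of sore throat, a different outcome.
- mR and mU, Visit 2 mean TSS of recovered and unrecovered patients: not given. By definition mR ≤ 2 and mU ≥ 3. Assumed pairs: (1, 4), (2, 3), (0.5, 5).
- d, mean improvement of unrecovered patients from Visit 2 to Visit 3: not given. Assumed 1 or 2 points.

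**Who is at Visit 3.** Group A: 0. Group B: 140 × (1 − r), which is 84 at r = 40%, 52 at 63% and 28 at 80%.

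**Formulas**

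- Visit 2 mean = r·mR + (1 − r)·mU
- Plotted Visit 3 mean = mU − d
- Whole-arm mean with recovered patients' Visit 2 values kept = r·mR + (1 − r)·(mU − d)
- The plotted mean rises only if d < r·(mU − mR)
- Plotted minus whole-arm mean = r·(mU − d − mR)

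**Central example: r = 0.63, mR = 1, mU = 4.** Visit 2 mean = 0.63 × 1 + 0.37 × 4 = 2.11. Break-even improvement = 0.63 × 3 = 1.89.

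| d | Plotted Visit 3 | Whole arm | Plotted minus whole arm |
|---|---|---|---|
| 1 | 4 − 1 = 3.00 (rise) | 0.63 + 0.37 × 3 = 1.74 | 0.63 × 2 = 1.26 |
| 2 | 4 − 2 = 2.00 (fall) | 0.63 + 0.37 × 2 = 1.37 | 0.63 × 1 = 0.63 |

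**Range of the break-even improvement, r from 40% to 80%**

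| mR, mU | Break-even d | Effect of a 1-point improvement |
|---|---|---|
| 2, 3 | 0.40 to 0.80 | falls at every r |
| 1, 4 | 1.20 to 2.40 | rises at every r |
| 0.5, 5 | 1.80 to 3.60 | rises at every r |

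In the first row with d = 1, mU − d equals mR, so the plotted and whole-arm means coincide at 2.00. The overstatement disappears only when continuing patients have caught up with recovered ones. The same algebra applies to VAS means, with the added assumption that patients unrecovered on TSS also have the higher VAS.

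**Laboratory data and ECG.** At Visit 2, Group B contributes only its recovered patients: 140 × r, or 56 at 40%, 88 at 63% and 112 at 80%. At Visit 3 it contributes only the remaining 84, 52 or 28. A line joining the two points joins two separate sets of patients.

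**Tests.** A between-arm p value at Visit 3 has no Group A data. The group-by-visit ANOVA has 2 × 3 = 6 cells, and the Group A/Visit 3 cell is empty by design.

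**The case against.** The strongest reply is that this is presentation only. The figure titles name neither Visit 3 nor a summary statistic. Table 18 shows counts per score category, not means. Table 17 has an n row that would expose the missing arm, SAP 3.8.3 says who attends, and a p value that cannot be computed misleads nobody. SAP 4.1.5 refers to laboratory and ECG results at Visit 1 and Visits 2–3, which could mean one post-baseline value. Secondary variables are of research interest only (SAP 4).

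Part of this stands. Inclusion of Visit 3 in the figures is inferred from the table shells, and the plotted mean is the natural reading rather than a stated one. But if Visit 3 is not meant to appear, nothing says so. An n row does not tell the reader that the subset was chosen on outcome. The pooled reading of SAP 4.1.5 conflicts with table shells that list three visits and with the visit-number factor in protocol 9.1.4. Carry-forward in SAP 3.6 belongs to the additional primary-endpoint analysis and does not govern these displays.

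It is also fair that stopping every display at Visit 2 would do harm: VAS change at the end of treatment is a pre-specified between-arm comparison (SAP 4.1.3) and must keep its place.

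**Conclusion.** The point holds as a fault of display and of the matching safety comparisons. The Group B Visit 3 TSS or VAS value describes perhaps 28 to 84 of 140 patients, selected on outcome. It can rise while all improve (2.11 to 3.00 against a whole-arm 1.74), and it overstates the arm mean by r·(mU − d − mR), which is 1.26 or 0.63 points in the central example. These sizes rest on assumed recovery shares, means and improvements. That Visit 3 has no Group A data, and that the Group B laboratory sets are disjoint, follows from the schedule alone.

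Three stronger readings are tempting and not supported:

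- *The comparator curve must rise.* It falls whenever d exceeds r·(mU − mR), as with d = 2 above, and the documents give none of these quantities.
- *The same artificial worsening appears in laboratory and vital-sign trends.* Laboratory values have no fixed direction that means worse, and neither do vital signs, except perhaps temperature. The laboratory fault is disjoint patient sets.
- *The efficacy conclusion is biased.* The primary endpoint and the TSS response and change endpoints are read on Day 4, and full recovery has its own display (Figure 5).

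**What to change.** - **TSS (Figure 1, Table 18):** end the between-arm display and p row at Visit 2.
- **VAS (Figure 6, Table 17):** show Visit 1, Visit 2 and one end-of-treatment value per patient (Visit 3 if attended, otherwise Visit 2). This keeps the pre-specified end-of-treatment comparison.
- **Laboratory data and ECG (Figures 8 and 9, Tables 8 to 14, SAP 4.1.5, ANOVA in protocol 9.1.4):** compare baseline with one end-of-treatment value per patient.
- **Vital signs (Figure 7, Table 7, SAP 4.1.5, ANOVA in protocol 9.1.4):** first reconcile protocol Table 1 with the visit text on whether unrecovered Group B patients are measured at Visit 2. If they are, compare the arms at Visit 2; if not, use the end-of-treatment value.
- **Visit 3:** show it only as paired Visit 2 and Visit 3 data (Visit 3 alone for laboratory data and ECG), with n, labelled *Group B, unrecovered at Day 4*.

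The cost is small: revised table and figure shells, and edits to SAP 4.1.5. Because the ANOVA is also in protocol 9.1.4, and SAP 1 envisages no change from the protocol, the change should be recorded under the procedure in protocol 9.6. Fewer visits are displayed, and the end-of-treatment value mixes Day 4 and Day 5 in Group B, which a footnote should state. No new data are needed.
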